7.3 Prior and Concomitant Medications

The number and percentage of subjects taking prior and concomitant medications will be summarized separately by generic name based on the World Health Organization (WHO) Drug Dictionary. A prior medication is defined as any medication taken prior to the date of the study drug initiation. A concomitant medication is defined as any medication that started prior to the date of study drug initiation and continued to be taken after study drug initiation or any medication that started on or after the date of study drug initiation, but not after the date of the last dose of study drug plus 39 weeks (273 days).

7.4 MRI

The MRI parameters from images obtained at Days 2 - 4 (defined as Baseline) will be summarized categorically with the number and percentage of subjects by treatment group as observed. The following will be summarized:

- Number and percentage of subjects with cerebral infarct location at Baseline, based on the categories of gray matter only (cortical and/or subcortical gray matter), white matter only (subcortical white matter), both (cortical and/or subcortical gray matter, and white matter), and other (none of the above)
- Number and percentage of subjects with cerebral infarct location at Baseline in the left hemisphere only, right hemisphere only, or both
- Number and percentage of subjects with cerebral infarct location at Baseline, based on the categories cortical, subcortical white matter, subcortical gray matter, other
- Vessel occlusion location at Baseline, based on the categories extracranial ICA, intracranial ICA or T lesion, MCA-M1, MCA-M2, MCA-M3, other
- mTICI score at Baseline, based on the categories 0, 1, 2a, 2b, 3

8.0 Efficacy Analyses

8.1 General Considerations

All efficacy analyses will be conducted in the FAS. Where noted, some analyses may additionally be conducted in the MMIAS. Because this is a small, exploratory, proof of concept study, p-values will not be presented. Where statistical models are noted, appropriate point estimates and 95% confidence intervals will be presented.

The primary analysis of efficacy endpoints will be performed after all ongoing subjects have completed the Treatment Period and an interim lock has been performed. This will be the final analysis for the efficacy endpoints during the Treatment Period.

Post treatment efficacy analyses will be completed following the final database lock.

Generally, "Baseline" refers to the last non-missing observation before the first administration of study drug. Where noted, Day 2-4 or Week 4 may be used as baseline. Unless otherwise specified, categorical variables will be summarized with the number and percentage of subjects in each category. Responder analyses will be presented with the number and percentage of subjects in each category, the difference in proportion of responders between the 2 treatment groups, and the 95% confidence interval for the difference based on Wald confidence limits, unless otherwise specified. Continuous variables will be analyzed using Mixed-Effect Model for Repeat Measures (MMRM) method. The dependent variable will be the visit value and baseline (pre-dose, Day 2-4 or Week 4, depending on the endpoint) will be included as one of the timepoints in the repeated measures. For analyses of change from baseline (pre-dose, Day 2-4 or Week 4, depending on the endpoint), this will be derived from a contrast of the group-level least squares (LS) means from the MMRM.

Unless otherwise specified, any subject who is randomized based on a wrong stratum will be analyzed according to the actual stratum the subject belongs to based on the eCRFs as noted in Section [7.2](#).

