4.2 Discussion of Study Design

Choice of Control Group

Approximately 120 subjects will be randomized to elezanumab 1800 mg or placebo in a 1:1 ratio. Use of placebo as a control is appropriate since participation in the study does not preclude subjects from receiving standard-of-care treatment for acute ischemic stroke including thrombolytic therapy and EVT.

Appropriateness of Measurements

Standard clinical and laboratory procedures will be utilized in this study. All patient-reported outcome (PRO) and clinician-measured scales are standard for assessing stroke severity and recovery in subjects with acute ischemic stroke. All clinical and laboratory procedures in this study are standard and generally accepted.

Suitability of Subject Population

This study will enroll subjects with acute ischemic stroke with an NIHSS total score of 7 to 21, inclusive, who are expected to have residual functional impairment following recovery after standard-of-care

treatment, and thus have the capacity to show a treatment effect in this initial proof-of-concept study. Subjects with milder stroke (as determined by NIHSS score or imaging) may experience notable spontaneous recovery, while subjects with more profound stroke have substantially increased risk of death and permanent disability and may be more likely to discontinue prematurely.

Inclusion of subjects who were treated with IV tPA and/or EVT will allow for assessment of the safety and efficacy of elezumab in a patient population more aligned with current standard of care for acute ischemic stroke. To maintain the ability to detect a potential treatment effect, subjects treated with IV tPA and/or EVT will be required to have an NIHSS total score of 7 to 21, inclusive, at least 1 hour after completion of the treatment(s). From a safety perspective, there are no expected pharmacokinetic or pharmacodynamic interaction between elezumab and IV tPA or EVT. Additionally, subjects are required to have no evidence of intracranial hemorrhage to minimize risk to subjects in the study.

Timing and Duration of Treatment

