- ✓ 7. NIHSS total score of 7 to 21, inclusive. NIHSS eligibility must be confirmed within 1 hour before randomization. For subjects treated with IV tPA \pm EVT, NIHSS must be confirmed \geq 1 hour after completion of all treatments and once any confounding effects of sedation or anesthesia have resolved.
- ✓ 8. No evidence of acute seizure at the onset of index stroke based on assessments conducted per standard of care. Subjects with evidence of seizure at onset of index stroke, but with imaging conclusively demonstrating an acute ischemic stroke are still allowed.
- ✓ 9. No evidence of acute myocardial infarction based on assessments per standard of care (e.g., elevated troponin levels, abnormal ECG).
- ✓ 10. In the judgment of the investigator, symptoms are not considered likely to resolve within the subsequent few hours (e.g., transient ischemic attack [TIA]).

Subject History

- ✓ 11. Subjects or their legally authorized representative confirms that before index stroke, there was no substantial impairment in subject's ability to perform activities of daily living (e.g., dressing, eating, walking, bathing, toileting) without assistance, as defined by a modified Rankin Score (mRS) of 0 to 2 before the index stroke.
- ✓ 12. Subjects with a history of previous stroke more than 3 months before enrollment are allowed if they are no longer experiencing ongoing functional recovery and mRS remains 0 to 2 prior to index stroke.
- ✓ 13. No known history before randomization of clinically significant medical conditions (other than current acute ischemic stroke) or any other reason, including any physical, psychological, or psychiatric condition that in the investigator's opinion would compromise the safety or interfere with the subject's participation in this study, or would make the subject an unsuitable candidate to receive study drug, or would put the subject at risk by participating in the study. Subjects with comorbid conditions that are, in the opinion of the investigator, clinically stable and not expected to meaningfully progress in the following 12 months may be considered eligible.
- ✓ 14. No known medical history of repeated episodes of complex migraine (e.g., weakness, vision, difficulty speaking). Subjects with history of complex migraine, but with imaging conclusively demonstrating an acute ischemic stroke are still allowed.

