7.3 Statistical Analyses for Efficacy

General Considerations

Analysis of the primary, secondary, and all other efficacy endpoints will be conducted on the FAS based on treatment as randomized, unless otherwise specified in the SAP.

The primary and secondary endpoints will be assessed using Bayesian methodology. No formal hypothesis tests will be performed. Additional efficacy endpoints will be summarized using descriptive statistics including the number of observations, mean, standard deviation, minimum, median, and maximum for continuous variables, and number and percent for categorical variables.

For continuous exploratory efficacy endpoints, the between-group treatment summary at each visit will be conducted using a mixed effects model with repeated measures (MMRM) including treatment group, visit, treatment-by-visit interaction, and stratification factors as fixed effects, the baseline values associated with the endpoint as covariates unless otherwise noted in the SAP. Missing data will not be imputed before performing the MMRM.

For binary efficacy endpoints, the frequency and percentage will be provided by treatment group. Missing values will be imputed as non-responders unless otherwise specified in the SAP.

Primary Efficacy Analysis

The primary analysis on NIHSS total score during the Treatment Period will be based on the AUC derived from an MMRM. The monthly-adjusted AUC of NIHSS total score for each treatment group will be obtained using the trapezoidal method and will be adjusted for month by dividing by 12. The MMRM model will include covariates of time since last known normal (≤ 12 hours, > 12 hours based on actual time of study drug initiation), IV tPA use, EVT use, main effects of treatment group and visit, and treatment-by-visit interaction. Each visit by a subject will serve as a repeated measure.

The posterior probability of the treatment group difference (with treatment showing greater improvement than placebo) in monthly-adjusted AUCs being greater than 0.6 using a noninformative prior will be calculated.

Secondary Efficacy Analysis

The secondary efficacy analysis is the proportion of subjects with a favorable outcome based on an mRS at Week 52 of 0, 1, or 2. The posterior probability of the treatment group difference (with treatment showing greater improvement than placebo) in responder rates being greater than 6.25% will be calculated using a non-informative prior.

Additional Efficacy Analyses

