2.3 Treatment Assignment and Blinding

Subjects will be randomized to elezanumab or placebo in a 1:1 ratio. Randomization will be stratified by intravenous (IV) tissue plasminogen activator (tPA) use (yes/no), treatment with endovascular therapy (EVT) (yes/no), and by time since "last known normal" (\leq 11 hours or $>$ 11) at the time of randomization.

The primary analysis of efficacy endpoints will be performed after the last subject completes the Week 52/Premature discontinuation visit. At this time, an interim database lock will occur, the randomization will be loaded into the database and the Data and Statistical Sciences department at AbbVie will perform the statistical analysis. Final safety analyses and post-treatment efficacy analyses will be performed following completion of the post-treatment period and database lock.

Study sites and subjects will remain blinded through the duration of the study.

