8.2 Handling of Missing Data

Missing data will be imputed using the following methods for the efficacy analyses:

- Non-Responder Imputation (NRI): the NRI analysis will categorize any subject who does not have evaluation during a specific visit window as a non-responder for that visit. Unless otherwise noted, this will be the primary approach for accounting for missing data in responder analyses.
- Generalized linear mixed model (GLMM): The model will include a logit link function to compare the probability of having responder between treatment groups of each visit of Day 2-4, Week 4, Week 8, Week 12, Week 24, Week 36, Week 52, and will include baseline NIHSS as a covariate and time from last known normal and initiation of first dose (≤ 12 hours, > 12 hours), tPA use (Y/N), EVT use (Y/N), visit, and treatment group as fixed effects. An unstructured variance covariance matrix will be used. The compound symmetry variance covariance matrix will be used if the model does not converge with unstructured matrix. The GLMM model relies on a missing at random (MAR) assumption.
- As Observed (AO): The AO analysis will not impute values for missing evaluations, and thus a subject who does not have an evaluation on a scheduled visit will be excluded from the AO analysis for that visit. AO will include all values collected in the study.
- MMRM: The repeated measures analysis will be conducted using a mixed model including observed measurements at all visits. The mixed model includes the categorical fixed effects of treatment, visit and treatment-by-visit interaction, main stratification factors at randomization, and the continuous fixed covariates of baseline measurement, unless otherwise noted. An unstructured variance-covariance matrix will be used; if the model does not converge, then a compound symmetry variance-covariance matrix will be used. Denominator degrees of freedom will be computed using the Kenward-Roger method. Parameter estimation is based on the assumption of data being missing at random and using the method of restrictive maximum likelihood. MMRM will be the primary approach in the analysis of continuous

variables unless otherwise noted. The MMRM model relies on a missing at random (MAR) assumption.

For all analyses related to the mRS, if a subject has a value of 6 (dead), this will be carried forward to future visits in the analysis. This will be applied to all mRS analyses, including the responder analysis as observed.

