8.4 Secondary Efficacy Analyses

The point estimate of the responder rate, odds ratio, and corresponding 95% confidence intervals will be derived from a generalized linear mixed model (GLMM) with a logit link function to compare the probability of having responder between treatment groups of each visit of Week 4, Week 8, Week 12, Week 24, Week 36, Week 52. The model will include time from last known normal and initiation of first dose (≤ 12 hours, > 12 hours), tPA use (Y/N), EVT use (Y/N), visit, treatment group as fixed effects, and visit as the random effect by subject. An unstructured variance covariance matrix will be used. The compound symmetry variance covariance matrix will be used if the model does not converge with unstructured matrix.

[figure not shown]

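### The default responder-rate difference is unadjusted: its 95% interval is valid, but using baseline NIHSS would make it modestly narrower at little cost

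*SAP*

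**What the plan says.** SAP 8.1 sets the default for responder endpoints, unless another section specifies otherwise. It gives counts and percentages by arm, then "the difference in proportion of responders between the 2 treatment groups, and the 95% confidence interval for the difference based on Wald confidence limits". It names no stratification or covariate. Under SAP 8.2 a subject without an evaluation in the visit window is a non-responder: "Unless otherwise noted, this will be the primary approach for accounting for missing data in responder analyses". SAP 8.6 applies the same non-responder rule and Wald difference to mRS 0-2 within each subgroup.

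Elsewhere the plan uses baseline information:

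- SAP 2.3 stratifies randomization by IV tPA, EVT and time since last known normal.
- The responder GLMM in SAP 8.2 "will include baseline NIHSS as a covariate and time from last known normal and initiation of first dose", together with tPA and EVT.
- The GLMM for the secondary endpoint in SAP 8.4 lists the three stratification factors but not baseline NIHSS. Its stated outputs are responder rates and an odds ratio with intervals. The readable text names no difference.
- In SAP 8.6, the ANCOVA for change in NIHSS adjusts for the stratification factors and baseline NIHSS. The mRS analysis in the same section adjusts for nothing.

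Protocol 7.3 frames the secondary endpoint on the difference scale, as a posterior probability for the difference "in responder rates being greater than 6.25% will be calculated using a non-informative prior".

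**The concern.** A difference in proportions that uses no baseline information carries all the outcome variance that baseline severity could have explained. In a trial of about 120 subjects the interval is wide, about 16 to 18 points either side, so precision available at no extra data cost is worth having. Baseline NIHSS should be available for essentially everyone, because Protocol 5.1 requires eligibility on that score to be confirmed within an hour before randomization. The plan already adjusts for it in other analyses and gives no reason for leaving it out here. What is at stake is precision on the scale in which the protocol expresses the secondary endpoint. The validity of the interval is not in question.

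**Working it through.** **Figure to reproduce.** There is none. The documents state no responder rate, interval width or power for a responder endpoint. The sample-size inputs are redacted and concern the NIHSS AUC.

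**Inputs from the documents.** "Approximately 120 subjects will be randomized to elezanumab 1800 mg or placebo in a 1:1 ratio" (Protocol 4.2), so 60 per arm. "NIHSS total score of 7 to 21, inclusive" (Protocol 5.1). Three binary stratification factors, so 2 × 2 × 2 = 8 strata.

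**Assumptions.** Control responder rate about 43%; NIHSS uniform over its range; permuted blocks of 4; shares of 35% tPA, 45% EVT and 40% early; and all prognostic strengths.

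**Step 1: raw Wald half-width.** 1.96 × √(2p(1−p)/60):

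- p = 0.3: 1.96 × √0.00700 = 16.4 points
- p = 0.4: 1.96 × √0.00800 = 17.5 points
- p = 0.5: 1.96 × √0.00833 = 17.9 points

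**Step 2: approximate effect of adjustment.** If covariates explain a share R² of outcome variance, the width is multiplied by √(1−R²), and the equivalent unadjusted trial size is 120/(1−R²).

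| R² | Width ratio | Equivalent N |
|---|---|---|
| 0.05 | 0.975 | 126 |
| 0.10 | 0.949 | 133 |
| 0.20 | 0.894 | 150 |

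**Step 3: simulation.** There were 2,500 trials per scenario, each run with and without a treatment effect. The raw Wald interval was compared with a standardized logistic risk difference with an influence-function standard error. Entries are mean 95% half-widths in points.

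| Log-odds per NIHSS point / per factor | R² | Raw | Three factors | Factors + NIHSS | Change, raw to last |
|---|---|---|---|---|---|
| 0 / 0 | 0 | 17.5–17.6 | 17.7–17.8 | 17.7–17.8 | about 1% wider |
| 0 / 0.5 | 0.04 | 17.6 | 17.3–17.4 | 17.3–17.4 | 1% to 2% narrower |
| −0.10 / 0.2 | 0.05 | 17.6 | 17.6–17.7 | 17.2–17.3 | about 2% narrower |
| −0.15 / 0.4 | 0.11 | 17.6 | 17.5–17.6 | 16.7–16.8 | about 5% narrower |
| −0.25 / 0.5 | 0.23 | 17.6–17.7 | 17.5–17.6 | 15.5–15.6 | about 12% narrower |

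Coverage was 93.5% to 95.9% for the raw interval and 94.1% to 95.4% with factors plus NIHSS. The factors alone never gained more than about 2%.

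The narrowing is real precision and not an optimistic standard error. The empirical SD of the estimate fell from 9.16 to 8.73 and from 8.71 to 8.30 points at R² 0.11 (about 5%). At R² 0.23 it fell from 8.75 to 7.92 and from 8.87 to 7.99 (about 10%). It did not fall when nothing was prognostic.

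**Step 4: other assumed effects.** Log-odds were EVT 0.4 to 0.6, tPA 0.2 to 0.4, early treatment 0.3 to 0.4 and NIHSS −0.12 to −0.18 per point, with 3,000 trials per scenario. With factors plus NIHSS, the mean standard error changed as follows:

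- One run: 0.0896 to 0.0856 (4.5% smaller) and 0.0894 to 0.0878 (1.8%).
- A second run: 0.0900 to 0.0836 (7.1%) and 0.0899 to 0.0872 (3.0%).

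A further simulation with weak and strong assumed effects gave empirical SDs of 0.0914 to 0.0897 and 0.0884 to 0.0829, a fall of about 2% and 6%. In sample terms, 1 − (0.0897/0.0914)² = 3.7% and 1 − (0.0829/0.0884)² = 12.1%.

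**The case against.** The case for leaving 8.1 alone is substantial.

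- **The gain is small and conditional.** On a half-width of 17.6 points, 2% to 7% is 0.4 to 1.2 points, which will seldom change a reading against 6.25. The documents give no prognostic strengths. Protocol 4.2 says milder strokes may recover spontaneously and more profound ones carry more death and disability. That passage explains the entry range, so it supports the direction of the effect but not its size within that range. This stands, and it is why the size is given as a range that includes zero.
- **The setting is descriptive.** The protocol plans no formal tests and the SAP presents no p-values. This stands and limits the priority.
- **Subgroups are sparse.** A five-term model could fail within the 8.6 subgroups. This stands, and the fix allows for it.

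Four stronger readings are tempting, and the documents do not support them.

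1. A reader might infer that ignoring the stratified randomization makes the interval wrong or too wide. Raw coverage was close to nominal. The mean standard error implied by the table (17.5 to 17.7 divided by 1.96, or 8.9 to 9.0 points) lies inside the range of empirical SDs, 8.71 to 9.33. Adjusting for the strata alone changes almost nothing.
2. A reader might infer that the secondary endpoint has no adjusted analysis. It has one: the 8.4 GLMM carries all three factors.
3. A reader might infer that the raw difference feeds the 6.25% posterior probability. The readable text does not say which estimate does, and parts of 8.4 and the text after it are not shown.
4. A reader might put any gap between the GLMM and raw results down to adjustment. The two also differ in missing-data handling (missing at random against non-response), use of repeated visits, and scale.

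**Conclusion.** The point holds as a matter of efficiency. The default responder difference is valid but uses none of the baseline information that neighbouring analyses use. With about 60 per arm, adjusting for the three factors and baseline NIHSS would narrow the 95% interval by about 2% to 7% under the assumed prognostic effects. The gain is nil (a cost of about 1%) if nothing is prognostic, and about 12% if the covariates explain about 23% of the variance. Baseline NIHSS supplies nearly all of it. These figures rest on assumed response rates, stratum shares, block size and covariate strengths, none of which the documents give as observed values. This is a cheap improvement, and no conclusion of the trial is at risk without it.

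**What to change.** In SAP 8.1, make the default responder difference under non-responder imputation a standardized (marginal) risk difference from a logistic model. The model would contain treatment, tPA, EVT, time since last known normal and baseline NIHSS, with the factors defined as in the SAP's other efficacy models. Give it a robust or delta-method 95% interval, and keep the raw counts and percentages in the table. State in advance that the raw difference with Wald limits is used in the 8.6 subgroups and wherever the model does not converge.

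The cost is a few lines of SAP text, slightly more programming, and a written fallback rule for sparse subgroups. No new data are needed.

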4 INVESTIGATIONAL PLAN

4.1 Overall Study Design and Plan

This is a 52-week, Phase 2a, randomized, double-blind, parallel-group, placebo-controlled, multicenter proof-of concept study to evaluate the safety and efficacy of elezanumab in subjects with acute ischemic stroke.

The schematic of the study is shown in [Figure 1](#). Further details regarding study procedures are located in the Operations Manual ([Appendix F](#)). Also see Section 5 for information regarding eligibility criteria.

The Screening Period is up to 24 hours since "last known normal" (the time before hospital arrival at which the subject was last known to be without the signs and symptoms of the current stroke or at his or her baseline state of health). Treatment with IV tPA and/or EVT will be allowed before randomization and will be recorded as a concomitant therapy.

[figure not shown]
Randomization will be stratified by IV tPA use (yes/no), by EVT use (yes/no), and by time since last known normal (≤ 11 hours or > 11 hours). The proportion of subjects enrolled who have EVT is targeted to be up to approximately 50% of the study population. A target of approximately 25% to 50% of subjects may be randomized within the time window of ≤ 11 hours since last known normal. Lastly, the proportion of subjects who enroll > 80 to 90 years of age is targeted to be up to approximately 30% of the study population. Eligible subjects will be randomized in a 1:1 ratio to receive either elezanumab 1800 mg or placebo as an IV infusion.

Administration of blinded study drug must be initiated as soon as possible but no later than 6 hours after randomization and done every 4 weeks thereafter through Week 48 for a total of 13 doses. The final double-blind Treatment Period study visit will be at Week 52. Subjects will have 2 post-treatment follow-up visits at 12 and 24 weeks after last dose of study drug, and a final follow-up phone call 39 weeks (5 half-lives) after last dose of study drug. All follow-up visits beginning at Week 4 during the Treatment Period and Follow-up Period will be allowed a window of \pm 7 days, and study procedures may be conducted over a period of 2 days. Unblinded safety data will be reviewed by an external DMC per the DMC Charter.

Final efficacy analyses will be performed after the last subject completes the Week 52 visit. Final safety analyses will be performed following completion of the post-treatment period and database lock.

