8.6 Efficacy Subgroup Analyses

Subgroup analysis of the change from baseline in NIHSS total score will be conducted for the following subgroups at Day 2-4, Week 4, Week 12, Week 24, and Week 52:

- Age (< 70, 70 - < 80, \geq 80 years at time of randomization)
- Sex (male, female)
- NIHSS total score at baseline (< 15, \geq 15)
- Time since last known normal based on actual study drug initiation time (\leq 12 hours, > 12 hours)
- tPA use (Yes, No)
- EVT use (Yes, No)
- Either tPA +/- EVT use (Yes, No)

This will be based on an ANCOVA as observed, with change from baseline as the dependent variable and including treatment and the stratification factors (except for the subgroup analysis corresponding to that stratification term, in which case that particular term will not be included in the model) as main effects and baseline NIHSS as a covariate. This will be based on the subsets for each subgroup separately, at the following time points: Day 2-4, Week 4, Week 12, Week 24, Week 52.

The number and percentage of responders based on the modified Rankin Scale (mRS 0-2) will be repeated for the subsets above using a non-responder imputation at Week 4, Week 12, Week 24, Week 52. The difference between treatment groups and corresponding 95% CI for the difference based on the Wald method will be produced.

A forest plot of each of the subgroups will be presented for each analysis at the time points Week 4, Week 12, Week 24, Week 52 based on the same outputs used in the tables.

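### Wald limits are the default interval for responder differences, with no fallback for small or sparse cells, so precision is overstated in the smallest mRS subgroups (minor)

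*SAP*

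**What the plan says.** SAP 8.1 presents responder analyses as counts and percentages, the difference in proportions, and "the 95% confidence interval for the difference based on Wald confidence limits". This is a default that holds unless another method is named. The same section says that p-values will not be presented.

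SAP 8.6 repeats mRS 0-2 for seven subgroup factors at Weeks 4, 12, 24 and 52 with non-responder imputation, and adds: "The difference between treatment groups and corresponding 95% CI for the difference based on the Wald method will be produced". A forest plot is drawn from the same outputs. Neither section names another method for small groups or for cells at 0% or 100%.

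The likely group sizes come from these statements:
- Protocol 4.2: "Approximately 120 subjects will be randomized".
- SAP 2.3: "Subjects will be randomized to elezanumab or placebo in a 1:1 ratio".
- Protocol 4.1, on subjects over 80: the proportion aged > 80 to 90 "years of age is targeted to be up to approximately 30% of the study population".
- Protocol 4.1, on early treatment (up to 11 hours since last known normal): "A target of approximately 25% to 50% of subjects may be randomized within the time window".

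The secondary endpoint has its own methods: a GLMM in SAP 8.4 and a posterior probability in Protocol 7.3. The visible text gives no expected responder rate for any endpoint.

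**The concern.** The Wald interval takes its standard error from the observed proportions alone. With few subjects, or with proportions near 0 or 1, that standard error is unstable and often too small. When each arm is at 0% or 100% it is exactly zero, and the interval shrinks to a point.

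This design makes some subgroups small. Non-responder imputation and the carrying forward of mRS 6 (SAP 8.2) also push observed mRS 0-2 rates down. A forest plot invites the reader to compare strata of unequal size by the width of their bars. If the bars are least trustworthy in the smallest strata, and no other measure of uncertainty is given, the reader will credit those strata with more precision than they have. No fallback is written down, so a change of method for sparse cells would have to be decided after the data are seen.

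**Working it through.** The plan states no figure to reproduce here: 95% is a nominal setting, and the sample-size inputs are redacted and concern the NIHSS AUC. The check is the exact coverage of the planned interval.

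**Group sizes**
- Full set: 120 / 2 = 60 per arm.
- Over 80: at most about 0.30 × 120 = 36, so 18 per arm. The SAP subgroup is 80 and over, so the match is approximate. The target is an upper one, so the group may be smaller.
- Early treatment: 0.25 to 0.50 × 120 = 30 to 60, so 15 to 30 per arm. The target uses 11 hours to randomization and the SAP subgroup uses 12 hours to dosing, so this match is also approximate.
- An equal split between arms within each subgroup is assumed.

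**Response rates** are assumptions, shown over a range.

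**Formulas**
- Wald: d ± 1.96 × √[p₁(1−p₁)/n₁ + p₂(1−p₂)/n₂], with observed p₁, p₂ and d = p₁ − p₂, without continuity correction.
- Newcombe: with Wilson limits (l₁, u₁) and (l₂, u₂) for the two arms, lower limit d − √[(p₁−l₁)² + (u₂−p₂)²], upper limit d + √[(u₁−p₁)² + (p₂−l₂)²].
- Coverage: the sum, over all pairs of responder counts, of the product of the two binomial probabilities for those pairs whose interval contains the true difference.

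**Coverage of the nominal 95% interval**

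| True rates (assumed) | Per arm | Wald | Newcombe |
|---|---|---|---|
| 40% v 55% | 60 | 94.7% | 94.8% |
| 40% v 55% | 30 | 94.4% | 94.6% |
| 40% v 55% | 18 | 92.7% | 93.7% |
| 40% v 55% | 15 | 91.0% | 93.6% |
| 40% v 40% | 18 | 93.7% | 94.0% |
| 20% v 10% | 18 | 92.9% | 96.4% |
| 10% v 5% | 18 | 89.4% | 98.8% |
| 10% v 2% | 60 | 92.3% | 97.0% |
| 10% v 2% | 18 | 84.5% | 99.5% |
| 5% v 5% | 18 | 99.1% | 99.1% |

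Over all pairs of rates between 20% and 80%, the lowest Wald coverage is 93.7% at 60 per arm, 91.4% at 18 and 91.1% at 15. The lowest Newcombe values at 18 and 15 per arm are 93.5% and 93.3%. Unequal arms change little: 12 v 18 subjects gives 92.4% for Wald at 40% v 55%.

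**Zero width**
- For rare responses the only case that matters is no responder in either arm.
- At 18 per arm and 5% v 5% its probability is 0.95^36 = 15.8%.
- At 10% v 2% it is 0.90^18 × 0.98^18 = 0.150 × 0.695 = 10.4%. Each of these samples misses the true difference, so they make up 10.4 of the 100 − 84.5 = 15.5 points of non-coverage.
- At 60 per arm and 5% v 5% it is 0.95^120 = 0.2%.
- For 0/18 v 0/18, Wald gives [0, 0]. The Wilson upper limit is 3.84 / (18 + 3.84) = 0.176, so Newcombe gives ±0.176.

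**Width at mid-range.** For 10/18 v 7/18, d = 0.167.
- Wald: standard error √(0.01372 + 0.01320) = 0.164, interval −0.155 to 0.488.
- Newcombe: Wilson limits 0.337 to 0.754 and 0.203 to 0.614. Lower limit 0.167 − √(0.0477 + 0.0506) = −0.147; upper limit 0.167 + √(0.0395 + 0.0345) = 0.439. Here the score interval is not the wider one.

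**The case against.** The strongest case against acting is that little in this trial turns on these intervals. The study is exploratory, without p-values or type I error control. The primary analysis is an MMRM, and the secondary endpoint has a GLMM and a posterior probability. The mRS subgroup tables add to the Protocol's own subgroup plan, which covers the primary endpoint only. All of this stands and sets the severity.

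Four stronger readings are tempting, and the documents do not support them.

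- *Every responder comparison rests on Wald.* SAP 8.1 allows exceptions, the secondary endpoint has other methods, and part of the efficacy text is redacted.
- *Coverage will generally be far below 95%.* Small size alone costs about 1 to 4 points at 15 to 18 per arm and mid-range rates. Rarity alone can have the opposite effect: equal rates of 5% at 18 per arm give 99.1%. The large shortfalls need small arms with rates that are both rare and unequal. The NIHSS responder definitions in SAP 8.3.4, which might be rare at early visits, have no visible subgroup breakdown. The documents therefore do not show that rare rates and subgroup sizes will meet.
- *Chance differences will look real.* At 18 per arm with equal true rates of 5, 10, 20, 30, 40 and 50%, Wald excludes zero in 0.9, 3.4, 6.0, 6.3, 6.3 and 6.6% of samples. Newcombe does so in 0.9, 3.3, 4.8, 5.0, 6.0 and 6.5%. The gap is at most about 1.3 points. At 10% v 2% the two exclude zero equally often (7.0%).
- *A collapsed interval creates a false signal.* With no responders in either arm it sits at zero, and the counts printed beside it show why. It claims certainty but does not suggest a difference.

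What survives is overstated precision in small or sparse cells.

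**Conclusion.** The point holds as a minor one. The default is adequate for the full set at mid-range rates. In subgroups of about 15 to 18 per arm it falls roughly 2 to 4 points short of nominal at an assumed 40% v 55%. It falls about 10 points short (84.5%) at an assumed 10% v 2% and 18 per arm, and it gives no usable interval when each arm is at 0% or 100%. Precision is therefore overstated most in the smallest strata of the mRS subgroup tables and forest plot, where it is the only uncertainty measure specified.

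The conclusion rests on assumed response rates, on subgroup sizes taken from enrolment targets whose cut-points differ slightly from the SAP subgroups, and on an equal split between arms. If mRS 0-2 rates in the subgroups are mid-range, only the modest shortfall applies.

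**What to change.** In SAP 8.1 and SAP 8.6, replace the Wald limits by one named score-type interval, either Newcombe (hybrid score) or Miettinen-Nurminen, for all responder differences. A single method throughout also settles sparse cells before unblinding, so no separate fallback rule is needed.

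The cost is an edit to two sentences and one option in PROC FREQ. Data collection, sample size and the primary analysis do not change. Some intervals become slightly wider and are no longer symmetric about the estimate. Newcombe is conservative for rare responses (99.5% at 10% v 2% and 18 per arm), so in such cells it will exclude zero no more often than Wald, and sometimes less often.
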